8.2.5. Analysis of Secondary Endpoints

All secondary endpoints will be summarized by treatment group on the ITT population. Raw means and changes from baseline will be displayed by treatment group, as appropriate.

The following continuous endpoints:

- Percent change in lower limb volume, as calculated based on manual circumference measurements, from baseline to visits 4, 5, and 6
- Percent change in circumferences from baseline to visits 3-6 that are measured at:
 - 10 cm above the center of the patella
 - at the center of the patella
 - 10 cm below the center of the patella
 - at the ankle; 1 cm above the medial malleolus
- Change of knee flexion angle from baseline to visits 3-6
- Change of knee extension angle from baseline to visits 3-6

Change of total ROM degrees, defined as the flexion angle minus the extension angle, from baseline to visits 3-6 will be analyzed using a mixed model repeated measures analysis (MMRM) with the same covariates outlined in the primary analysis. General linear mixed models and/or paired t-tests at each week may also be performed.

The average pain and worst pain in each leg in the last 24 hours using an NPRS (numerical pain rating scale) of 0-10 (daily for 4 weeks post-surgery, then weekly for weeks 5-12) will be analyzed in the following two ways:

- An AUC, or area under the receiver operating characteristics (ROC) curve, will be calculated for daily pain scores for each knee using a general linear mixed model with site, treatment, and knee side (left/right) included in the model as

covariates while adjusting for correlations from the within-subject comparisons over time. A model with an AUC of at least 0.70 will be considered adequate.³⁷

- Weekly pain scores (average pain scores for each week (weeks 1-4) and reported weekly pain scores (weeks 5-12)) will be analyzed using an MMRM with site, week, treatment, knee side (left/right), and treatment by week included in the model as covariates while adjusting for correlations from the within-subject comparisons over time. The covariance structure will be selected based on the lowest Akaike Information Criterion value. Raw means, LS Means, including 95% confidence intervals, will be presented by treatment group.

A Chi-square, McNemar's, or Fisher's test as appropriate will be used to analyze the following endpoints:

- The incidence of SSCs by visits 5 and 6
- Scar cosmesis assessment at visits 3-6

Additional details will be specified in the Statistical Analysis Plan.

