8.4. Open-Label Study Reporting Results

All precautions will be taken to avoid introducing any form of bias during the conduct of the study. While the study is ongoing, summary statistics by treatment arms across all sites may be limited to a small group not involved in the daily operations of the study. Treatment arms may be masked in the summary reports or outputs (tables, listings, and figures) if needed. Summary statistics during the conduct of the study will not be shared with investigators and clinical sites. Upon study completion, the full results will be shared with all investigators and clinical sites.

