8.6. Statistical Analysis Plan and Changes in Analyses

A Statistical Analysis Plan (SAP) containing full details of the statistical analyses and execution will be prepared for this study. The SAP (SAP) will be finalized prior to locking

the study database and the final analysis. Any changes from the planned analyses in this protocol or SAP will be noted in the Clinical Study Report (CSR).

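### The first planned pain analysis (Section 8.2.5) defines its AUC as a ROC area with a 0.70 adequacy rule, which cannot be run on 0-10 pain scores and does not compare the treatments

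*Combined protocol and SAP*

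**What the plan says.** Section 4.12 has subjects rate average and worst pain for each leg on a 0-10 numerical scale, daily for four weeks after surgery and weekly for weeks 5-12. Footnote 4 of Section 5.1 starts the diary on the day after surgery.

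Section 8.2.5 gives two analyses for these scores.

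- First analysis: "An AUC, or area under the receiver operating characteristics (ROC) curve, will be calculated for daily pain scores for each knee". The model behind it is described in these words: "using a general linear mixed model with site, treatment, and knee side (left/right) included in the model as". Treatment thus enters as one covariate among three. The only criterion attached to the result is: "A model with an AUC of at least 0.70 will be considered adequate".
- Second analysis: "Weekly pain scores (average pain scores for each week (weeks 1-4) and reported weekly pain scores (weeks 5-12)) will be analyzed using an MMRM". The terms of that model cover site, week, treatment and knee side, plus the interaction of treatment and week. LS means with 95% confidence intervals are reported for each treatment group.

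The section closes with "Additional details will be specified in the Statistical Analysis Plan". On timing, Section 8.6 places the SAP ahead of database lock: "The SAP (SAP) will be finalized prior to locking". No separate SAP text is among the documents reviewed.

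**The concern.** The abbreviation AUC has two unrelated meanings here. In pain trials it usually means the area under the score-by-time curve, a summary of total pain over a period. In classification it means the area under a ROC curve, a measure of how well a score separates two classes. The protocol spells out the second meaning and attaches a threshold that belongs to it, yet the data and the model suit the first.

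An analyst following the text would have to invent a binary outcome and a classifier. The result would be a statement about the adequacy of a model, not an estimate of how pain differs between the knee treated with ciNPT and the control knee. Someone therefore has to choose a replacement. This is an open-label study, and Section 8.4 foresees by-arm statistics before completion: "While the study is ongoing, summary statistics by treatment arms across all sites may be limited to a small group". If the choice is made after pain results by arm have been seen, it is no longer a pre-specified analysis.

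**Working it through.** The plan derives no figure here. The 0.70 is a stated threshold, so there is nothing to reproduce. The check is whether the analysis can be executed under each meaning of AUC.

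**Reading 1: ROC area, as written.**

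- Needed: a binary outcome and a score that ranks observations against it.
- Given: an outcome on a 0-10 scale (Section 4.12), with no cut-off or event defined for pain in any section, and a linear mixed model for that outcome (Section 8.2.5).
- Result: the model returns fitted means and treatment coefficients. It returns no ROC curve.

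The one binary variable to hand is treatment itself. Suppose the ROC area measured how well a daily score separates the two treatments. Under normality, and ignoring the pairing of knees, the area is c = Φ(δ / (SD × √2)), where δ is the mean difference. The documents give no pain SD, so 2.0 and 2.5 are assumed.

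- δ = 0: c = 0.50.
- δ = 1, SD 2.0: c = Φ(1 / 2.83) = 0.64.
- δ = 1, SD 2.5: c = Φ(1 / 3.54) = 0.61.
- c = 0.70 requires δ = 0.524 × SD × √2, which is 1.48 points (SD 2.0) or 1.85 points (SD 2.5).

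Even on this invented construction, a real one-point difference would fall short of 0.70. The rule is not a test of treatment effect.

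**Reading 2: area under the pain-time curve for each knee.**

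- Inputs: scores 0 to 10; 28 daily scores on Days 1-28 (Sections 4.12 and 5.1), hence 27 one-day intervals.
- Trapezoidal maximum: 10 × 27 = 270. The range is 0 to 270.
- A constant one-point treatment difference: 1 × 27 = 27.
- A threshold of 0.70 is a mean score of 0.70 / 27 = 0.026 points, or 0.70 / 270 = 0.26% of the maximum.
- A knee scored 1 on one interior day and 0 on the other 27 days has area ½ + ½ = 1.0, which already exceeds 0.70.

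The area itself could be computed, but the 0.70 rule has no meaning on this scale.

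**Set side by side.** The threshold fits only the ROC reading. The data and the model (one value for each knee; site, treatment and knee side; no day term) fit the pain-time reading better. Neither reading makes the whole bullet executable.

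**What remains for pain.** The weekly model has treatment and treatment-by-week terms, so the difference between arms in each week, and any average of those differences, can be estimated from it.

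**The case against.** The strongest reply is that this is a slip of wording. The AUC is calculated for each knee and the model has no day term, which is how one would analyse a single summary per knee. Drop the ROC gloss and the 0.70 sentence, and an ordinary analysis of a pain-time area is left. That is plausible and may well be what was intended, but the protocol does not say it, and the 0.70 sentence agrees with the gloss.

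A reader might argue that the closing phrase rules out a single summary per knee, because it speaks of "covariates while adjusting for correlations from the within-subject comparisons over time". It does not. The same phrase stands word for word in the weekly bullet and reads as standard text.

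A reader might also infer that this bullet is singular in naming no treatment difference. That is not supported either. The weekly model and the primary analysis (Section 8.2.4) likewise promise LS means by treatment group without naming the difference, and Section 8.2.1 sets two-sided tests at 0.05 with 95% confidence intervals for the plan in general. What is particular to the first pain analysis is that its stated criterion concerns model adequacy.

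Finally, further detail is deferred to the SAP, which is due before database lock, and Section 8.4 allows arms to be masked and bars sharing interim summaries with sites. This lowers the risk. It does not settle the point, because the SAP would have to replace a definition, not merely add detail to it.

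**Conclusion.** The point holds. As defined, the first pain analysis cannot be carried out, and its only stated criterion says nothing about treatment. That rests on the wording alone. The 0-270 scale assumes a complete Day 1-28 diary and the trapezoidal rule; the ROC illustration rests on assumed SDs and normality.

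The reach is small: one of two analyses for each of two secondary endpoints in a pilot study. A reader might infer that the trial has no usable comparison of pain, or that its conclusions are in doubt. The documents do not support this. The weekly model supports the comparison, and the primary endpoint, sample size and safety analysis do not depend on the faulty text. The documents give no expected pain difference or SD, so any effect on the pain conclusions cannot be sized. A later correction in the SAP cannot be ruled out. Severity is minor to should-fix.

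**What to change.** Before database lock, and before any by-arm pain summary is reviewed:

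1. Delete the ROC definition and the 0.70 rule from Section 8.2.5.
2. Replace them with wording such as: *The treatment difference (ciNPT minus control), averaged with equal weight over weeks 1-4, will be estimated from the weekly MMRM with a 95% CI, separately for average and worst pain.* In symbols, the contrast is (d1 + d2 + d3 + d4) / 4, where dw is the difference in week w.
3. If a per-knee pain-time area is kept, define it as the area under the Day 1-28 score curve divided by the time covered (27 days for a full diary), which returns it to the 0-10 scale. Compare arms with the site, treatment and knee-side mixed model already stated, with subject as a random effect, and report the difference with a 95% CI. Label it supportive.
4. For that area, state how missing days and diaries that stop early are handled. Restricting it to complete diaries is not a good answer: Section 4.4.2 ends data collection at withdrawal, while Section 8.2.5 places secondary endpoints on the ITT population.

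The cost is protocol or SAP wording and minor programming. The contrast uses a model already planned and scores already collected, with no change to sample size or visits.

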4.15.2. Scar Cosmesis Assessment

The assessments of scar quality in this study will be performed by the investigator or investigator-designated physician for each knee using the Manchester Scar Scale.³³ This visual analog scale includes clinical assessment of the scar color, contour, texture, and distortion.

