8.2.4. Analysis of Primary Endpoint

The primary endpoint is the percent change in lower limb volume, as calculated based on manual circumference measurements, 5-7 days after total knee arthroplasty (TKA) when using the PREVENA RESTOR ARTHRO•FORM™ Incision Management System

compared to the control. The lower limb volume is calculated using the Frustum formula^{35;36}:

$$Volume = \sum \pi(x_{(i+1)}^2 + x_i^2 + x_i \cdot x_{(i+1)}) \left(\frac{h}{3}\right)$$

where x_i and x_{i+1} are the circumferences of two consecutive sections along the limb, and h is the length of the interval between the two measurements on the limb. The lower limb volume is determined by calculating the sum of the volumes of all sections. The percent change of the lower limb volume is defined as the difference of lower limb volume from baseline (pre-op) to postoperative Day 5-7, divided by the baseline measurement of lower limb volume, multiplied by 100.

A general linear mixed model repeated measures analysis (MMRM) will be used to analyze the primary endpoint with covariates: site, study visit, treatment, knee side (left/right), baseline lower limb volume, baseline BMI category ($<30 \text{ kg/m}^2$, $\geq 30 \text{ kg/m}^2$), and treatment by study visit. Knee side will serve as a repeated-measure factor to account for the correlations between left knee and right knee on the same subject, and the subject variable will also be specified to identify those observations that are to be correlated. Raw means, LS Means, including 95% confidence intervals, will be presented by treatment group. The ITT analysis set will be used for the primary analysis.

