8.3.2. Randomization

All subjects who meet all inclusion criteria and no exclusion criteria will be randomized in a 1:1 ratio to receive the PREVENA RESTOR ARTHRO•FORM™ Incision Management System or the control in either right or left knee. Each subject will receive both treatments (one treatment per knee). A randomization schedule, including randomization numbers and treatment assignments, will be generated and maintained centrally in the web-based clinical database management system. Once randomized, a subject's assignment cannot be altered or changed; a subject should not be randomized twice. The randomization schedule will be kept blind to any person who is involved in the daily operations of the study. It will only be accessible to the study biostatisticians who generate and review the schedule, and the vendor's team members (if an EDC vendor is utilized) who are involved in reviewing the schedule and uploading the schedule.

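### None of the three tests named for scar cosmesis suits a paired visual-analog score; for SSC incidence a suitable test is listed, but so are two that ignore the pairing

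*Combined protocol and SAP*

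**What the plan says.** Section 8.2.5 gives a single rule for two secondary endpoints: "A Chi-square, McNemar's, or Fisher's test as appropriate will be used to analyze the following endpoints". The endpoints are "The incidence of SSCs by visits 5 and 6" and "Scar cosmesis assessment at visits 3-6". There is no rule for choosing among the three tests, and further detail is left to a separate SAP.

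The scar is rated "for each knee using the Manchester Scar Scale" (section 4.15.2). The next sentence there reads: "This visual analog scale includes clinical assessment of the scar color, contour, texture, and distortion". No cut-point, responder definition or set of categories is given.

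The design is within-subject. Section 8.3.2: "Each subject will receive both treatments (one treatment per knee". The primary analysis in section 8.2.4 takes this into account: "Knee side will serve as a repeated-measure factor to account for the correlations between left knee and right knee on the same subject". Within section 8.2.5, the mixed-model and paired t-test wording belongs to the limb-volume, circumference and range-of-motion changes, and the pain analyses adjust for within-subject correlation. Scar cosmesis is in neither group.

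**The concern.** A scar score on two knees of the same person is a paired, roughly continuous outcome measured at four visits. The phrase about using a test where appropriate helps only if one of the listed tests is appropriate, and for the score as described none is. To apply any of them the analyst must first turn the score into categories. Two of the three then discard the pairing as well.

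SSC incidence is different. It is binary per knee, so McNemar's test is suitable as it stands. What is left open there is the choice: a common habit is to use Fisher's test when events are few, and that would drop the pairing.

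At stake is the efficiency that section 1.3 gives as a reason for the bilateral design, and an analyst's choice that could be settled late. Section 8.6 requires the SAP only before database lock, and the study is open-label (section 8.4).

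**Working it through.** **1. The plan's own figure, to fix the number of pairs.** Section 8.3.1 gives means of 13.6% and 8%, SD 9.2%, 80% power, type I error 0.05, a two-sample t-test and 15% dropout. The standardised difference is (13.6 − 8)/9.2 = 0.609. The t-test needs 43.35 per arm, so 44 (power 80.6%). 44/0.85 = 51.8, so 52, as stated. With one knee per arm from each subject, that leaves 44 complete pairs. The protocol gives no effect size, SD, event rate or correlation for scar or SSCs, so those below are assumptions.

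**2. Tests against data.**

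| Test | Outcome needed | Uses the pairing | Scar score as described | SSC incidence |
|---|---|---|---|---|
| Chi-square | categories | no | no | ignores pairing |
| Fisher's | categories | no | no | ignores pairing |
| McNemar's | binary | yes | only after an undefined split | suitable |

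**3. Scar score.** For a difference of d SDs and between-knee correlation ρ, the paired effect is d/√(2(1 − ρ)), and approximate power is Φ(effect × √44 − 1.96). At d = 0.4 and ρ = 0.5 the effect is 0.4/√1 = 0.4, and 0.4 × 6.633 − 1.96 = 0.69, giving about 75%. Simulation with bivariate normal scores, 44 pairs, two-sided 0.05, the split at the control mean and 6,000 runs per row (Monte Carlo error up to about 1.3 points) gives:

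| d (SD) | ρ | Paired t | Signed-rank | Exact McNemar's, split | Chi-square, split | Fisher's, split |
|---|---|---|---|---|---|---|
| 0.4 | 0.3 | 60% | 58% | 29% | 29% | 21% |
| 0.4 | 0.5 | 74% | 72% | 33% | 27% | 19% |
| 0.4 | 0.7 | 92% | 91% | 40% | 25% | 16% |
| 0.5 | 0.3 | 79% | 77% | 44% | 45% | 35% |
| 0.5 | 0.5 | 90% | 89% | 49% | 44% | 33% |
| 0.5 | 0.7 | 98% | 98% | 60% | 44% | 31% |
| 0.6 | 0.3 | 91% | 90% | 59% | 61% | 51% |
| 0.6 | 0.5 | 97% | 97% | 65% | 61% | 51% |
| 0.6 | 0.7 | 100% | 100% | 75% | 62% | 50% |

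With no true difference, rejection rates over the same correlations are 4.4% to 5.1% (signed-rank), 2.4% to 2.8% (exact McNemar's), 0.5% to 2.6% (Chi-square) and 0.2% to 1.3% (Fisher's).

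**4. SSC incidence.** With equal rates, the true variance of the difference is (1 − φ) times what an unpaired test assumes, where φ is the within-subject correlation. At φ = 0.3 the unpaired statistic has SD √0.7 = 0.837, so it passes 1.96 with probability about 1.9% rather than 5%. Simulation with 44 pairs and a 20% rate in both arms, at φ = 0 / 0.3 / 0.6:

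- Chi-square 5.3% / 2.2% / 0.4%
- Fisher's 2.5% / 0.8% / 0.1%
- exact McNemar's 2.7% / 2.2% / 1.2%
- asymptotic McNemar's 4.6% / 4.3% / 5.1%

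Power at assumed rates of 30% and 10%:

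| φ | Chi-square | Fisher's | Exact McNemar's | Asymptotic McNemar's |
|---|---|---|---|---|
| 0 | 68% | 56% | 56% | 65% |
| 0.3 | 71% | 57% | 72% | 80% |

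An illustration, constructed to show that the choice can matter: 12/44 against 5/44 with 8 and 1 discordant pairs. Exact McNemar's p = 2 × (1 + 9)/2⁹ = 0.039; Fisher's p = 0.103; uncorrected Chi-square p = 0.059.

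**The case against.** The best defence is that the authors plainly know the design is paired, that McNemar's is on the list, and that a separate SAP is promised. For SSCs this largely succeeds: a reader might infer that the planned SSC method is wrong or missing, but the protocol names a valid one and merely fails to require it. For scar it does not succeed, because no listed test suits the score. The separate SAP may define a cut-point; all that can be said here is that the protocol does not.

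Three stronger readings are also tempting and should be set aside.

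- *That the unpaired tests threaten false positives.* With positive correlation between knees they are conservative, so the harm is inefficiency.
- *That every listed test needs a two-way split.* Chi-square and Fisher's tests accept several categories. The two-way split modelled above is one possible reading, and the protocol does not prescribe it.
- *That a real cosmetic difference would usually be missed.* This depends on the assumed effect. At 0.6 SD even exact McNemar's on the split score has 59% to 75% power.

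Section 8.2.5 also plans raw means by group as appropriate, so the scores need not disappear from the report. These are secondary endpoints in a study titled a pilot.

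**Conclusion.** The point stands for scar cosmesis: the protocol assigns it no test that suits a paired score. Under the assumptions shown (44 complete pairs, normal scores, 0.4 to 0.5 SD, correlation 0.3 to 0.7), using a split score with a listed test instead of a paired score analysis costs roughly 30 to 50 percentage points of power with exact McNemar's and more with Fisher's. The direction is secure. The size is only indicative, since the documents supply no scar effect, SD or correlation.

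For SSC incidence the point is smaller. The wording permits two tests that ignore the pairing alongside one that respects it; the loss is nil when knees are uncorrelated and grows with correlation. Nothing here touches the sample size or the primary analysis.

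**What to change.** **Scar score, Visits 3-6.** Name a mixed model with site, visit, treatment, knee side and treatment by visit, and subject as the correlated unit. This has the same shape as the plan's own weekly pain model. The primary model should not simply be reused: it carries baseline limb volume, whereas scar has no pre-operative baseline (section 5.1 starts it at Visit 3). A Wilcoxon signed-rank test at each visit is an acceptable alternative. State which score is analysed, since section 4.15.2 lists components without saying how they combine.

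**SSCs by Visits 5 and 6.** Name McNemar's test with a paired difference in proportions and its 95% CI, and delete Chi-square and Fisher's. Say in advance whether the exact or asymptotic form is used; the exact form is itself conservative here.

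**Incomplete pairs.** Section 8.2.1 allows subjects with one treated knee. State that for SSCs they are summarised descriptively and do not enter the paired test.

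The cost is protocol and SAP wording only, best done well before database lock; no new data or subjects are needed.

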
8.2.6. Exploratory Analyses

The exploratory endpoints are as follows:

- the percent change in lower limb volume, as calculated based on three-dimensional (3D) imaging, from baseline to visits 3-6
- Knee-related QoL questionnaire (new Knee Society Knee Scoring System) at visits 4, 5, and 6
- Ability to perform a straight leg raise at visits 4, 5, and 6

Any additional exploratory endpoints and all exploratory endpoint analyses will be outlined in the SAP. Because the analyses are exploratory, no adjustment will be made for multiple comparisons.

